## STUDY PROTOCOL

### PRIMARY STUDY OBJECTIVES

**Aim 1:** Determine the effects of social determinants of health for adolescent HPV vaccine completion (age, sex, race/ethnicity, insurance type, area deprivation index for residence, and distance to clinic) within a 14-month period using EHR data from retrospective chart reviews.

### SECONDARY STUDY OBJECTIVES

**Aim 2:** Explore barriers and facilitators to vaccine completion by describing parent and adolescent experiences with the HPV vaccine, including individual, relationship, and community level determinants influencing vaccine completion, and integrating interview data with social determinants explored in Aim 1.

### PURPOSE OF THE STUDY AND HYPOTHESES TO BE TESTED

The purpose of this study is to identify individual-, relationship-, and community-level determinants of HPV vaccine completion among adolescents ages 11 to 14 who received one dose of the vaccine, and barriers and facilitators to completion as described by parents and adolescents. The following hypothesis will be tested for Aim 1:

**H1:** Younger adolescents, boys, racial/ethnic minorities, adolescents without health insurance and those living in areas with high deprivation and far distances from the clinic will be less likely to complete the HPV vaccine series.

### BACKGROUND & SIGNIFICANCE

The human papillomavirus (HPV) is the most prevalent sexually transmitted infection in the U.S. and causes nearly 90% of cervical and anal cancers and 70% of vaginal, vulvar, penile and oral cancers (Centers for Disease Control and Prevention (CDC), 2016; Gillison, Chaturvedi, & Lowy, 2008; Reiter et al., 2013). The HPV vaccine, Gardasil 9, is recommended for administration to adolescents before engaging in sexual activity to prevent exposure against nine commonly transmitted strands. Despite the efficacy of the vaccine in preventing HPV and associated cancers, HPV vaccine rates remain low, with initiation rates (i.e. receive 1 dose) at 65% among adolescent girls and 56% among adolescent boys. Completion rates (i.e. receive 2 or 3 doses depending on certain age groups) are significantly lower at 49.5% and 37.5% among adolescent girls and boys respectively (CDC, 2017; Walker et al., 2016).

Recently, the Advisory Committee on Immunization Practices (ACIP) lowered the number of required doses for adolescents (ages 11 to 14 years) to 2 doses based on evidence demonstrating sustained immunogenicity after the second dose (Meites, Kempe, & Markowitz, 2016). However, since these changes occurred in late 2016 (Walker et al., 2016), current completion rates do not reflect vaccine completion solely for this age group (Meites et al., 2016). Further, the vaccine remains on a 6 to 12-month administration schedule, requiring adolescents to return to clinics to receive subsequent doses (Meites et al., 2016). Given the gap between vaccine initiation and completion rates it is believed that disparities in HPV vaccination might be exacerbated due to social determinants. To date, most of the literature on HPV vaccination in adolescence has largely focused on individual-level determinants influencing parents to refuse vaccination and initiate the vaccine series, including parents' beliefs, attitudes, awareness (Tsui

et al., 2013; Askelson et al., 2010; Hertweck et al., 2013) and knowledge about the HPV vaccine (Dempsey et al., 2012; Thomas et al., 2012; Reiter, Katz, & Paskett, 2013), insurance coverage (Tsui et al., 2013; Ylitalo, Lee, & Mehta, 2013; Reiter et al., 2009), and family socioeconomic status (Polonijo et al., 2016; Gerend, Zapata, & Reyes, 2013; Perkins et al., 2013). Contrary to research on social factors influencing health (World Health Organization (WHO), 2018; Marmot, 2017; Braveman & Gottlieb, 2014), adolescents with public health insurance, who were Black or Hispanic descent, and lived in low-income communities are more likely to receive the first dose of the HPV vaccine series. While these findings hold promise for addressing disparities related to vaccine initiation, they may not reflect potential determinants influencing vaccine completion. For example, although Black and Hispanic adolescents are just as likely to initiate the vaccine at the same rate as non-Hispanic White adolescents, they are less likely to complete the vaccine series (Reiter et al., 2013; Ylitalo et al., 2013; Spleen et al., 2012; Bartlett & Peterson, 2011). Thus, further exploration is warranted to identify which social determinants influence vaccine completion.

## DESIGN AND PROCEDURES

**Design:** This study will use a parallel mixed method design that combines retrospective chart reviews and individual qualitative interviews to examine the effects of social determinants of health (SDH) for HPV vaccine completion among adolescents and explore parents and adolescents' experience with the HPV vaccine including perceived barriers and facilitators to completing vaccine series. Chart reviews will be used to identify individual and community-level characteristics of adolescents (age 11 to 14 years) and determine vaccine completion by whether the second recommended dose was received within a 14-month period. A descriptive qualitative design will be used for Aim 2 to describe barriers and facilitators to vaccine completion among parents and adolescents who did or did not complete the vaccine series.

**Procedures: Aim 1.** A request for waiver of informed consent will be submitted to the IRB to access previously collected data on adolescents' charts retrospectively. The PI will collaborate with a research data manager to abstract eligible electronic health records through the Maestro Care database. Data pulled from the Maestro Care database will be imported and stored in a secure folder in PACE, a highly protected network space where users can analyze and work with identifiable protected health information. Data on adolescents' HPV vaccine completion will be recorded on data collection forms using the number of vaccine doses received, the date in which the vaccine doses were administered, and clinic location in which the vaccine doses were received. The North Carolina Immunization Registry (NCIR) will be used to verify HPV vaccine completion in the event that the adolescent receives any of the vaccine doses outside of the Duke University Health System (DUHS) network. The NCIR is a secure, web-based database where healthcare providers report immunizations administered to patients within North Carolina. I have gained view-only access to the NCIR through the selected pediatric clinic and will only use the database to record the number of HPV vaccine doses, the dates in which the doses were administered, and clinic location in which the doses were received for eligible adolescent charts for Aim 1. A cohort of adolescents will be created by examining charts of all adolescents ages 11 to 14 who received 1 dose of the HPV vaccine from January 2017 to December 2017. This cohort will be followed from January 2018 to February 2019 to assess vaccine completion within a 14-month period documented in the adolescents' electronic medical chart. Data from chart reviews will be partially de-identified; zip codes, addresses from participants and the person listed as the emergency contact, and the dates of HPV vaccine administration will be the only identifiable data recorded from the chart reviews. Zip codes will be recorded to determine

the area deprivation index of the adolescent's place of residence. Addresses will be recorded to calculate the number of miles for the distance from clinic variable. Lastly, the date of HPV vaccine administration will be used to determine the number of months between receipt of the first and second dose within a 14-month period. However, once area deprivation index values have been determined, the distance from clinic miles calculated using geographic information systems (GIS) software, and the date of vaccine administration have been converted to months (e.g. 1st dose = 1 month; 2nd dose = 8 months from first dose) participants' zip codes, addresses, and date of vaccine administration will be deleted from the dataset. Each eligible adolescents' chart will be provided with a subject ID number. To minimize the risk of loss of confidentiality, all data will be stored and secured in the PACE network. Additional data (i.e. analyses results) will be stored in an electronic, password-protected share drive at Duke University School of Nursing and will be backed up daily. Only the study team will have access to both the share drive and PACE network.

**Procedures: Aim 2.** Purposive sampling will be used to recruit key informants from the Duke Primary Care Pediatrics at Roxboro Road to complete individual interviews on barriers and facilitators to HPV vaccine completion. A request for waiver of informed consent will be submitted to the IRB to use adolescents' charts and the NCIR database to prescreen for potential eligible subjects and gather contact information through chart reviews prior to obtaining consent from parents and assent from adolescents. The NCIR will be used for screening purposes to determine vaccine completion by identifying whether adolescents received any HPV vaccine doses at other clinics outside of the DUHS network, or if the adolescent is a new patient to the clinic and does not have their immunization records established with their chart. Names, date of birth, and/or EHR chart numbers of eligible participants will be used to search for adolescents in the database; however, will not be recorded. Key informants will include male or female adolescents who completed the vaccine series or began the series but did not finish it, as well as their parents (n=32). To ensure informational representation, 16 parents and adolescents who completed the vaccine series (Completers) and 16 parents and adolescents who did not complete the vaccine series (Non-completers) within 14 months will be recruited. Both English and Spanish-speaking participants will be recruited. For Spanish-speaking participants, an approved Duke University Health System, Spanish interpreter provided by the selected pediatric clinic will be used to assist with translating the study eligibility criteria, information about the study, and contact information from the participants. Face to face, semi-structured, individual interviews will occur at one-time point in a private location at the preference of participants (i.e. reserved room at Duke University campus or local library, home, etc.) and will be conducted in either English or Spanish. For Spanish-speaking participants, a bilingual data collector will be assigned for the interview. The bilingual data collector is a native Spanish speaker and proficient in the Spanish language. All interviews will last approximately 45 minutes to 60 minutes and will be recorded using a recorder device to be transcribed verbatim. Interview data will be transcribed verbatim from an electronic recording device by a hired, bilingual transcriptionist through a Duke University School of Nursing (DUSON) approved vendor. I will double-check the accuracy of the transcribed text. Audio recordings will be uploaded in a secure folder on an electronic share drive at DUSON which only key study personnel will have access to. These files will be sent to the transcriptionist using Duke Box, a secure method of sharing data that is approved by the Duke IRB. During transcription, participants' names and other identifiable information (i.e. provider's name, clinic name/location, etc.) will be removed from the text. Audio recordings will be destroyed after qualitative data analysis has been completed. Field notes will capture parents' and adolescents' emotions and

behaviors as responses are provided during the interviews. De-identified demographic data (e.g., age, race/ethnicity, and sex) collected after interviews will be recorded on paper surveys then entered into a password-encrypted Excel spreadsheet for descriptive statistics. Informed consents, child assents, transcribed text, field notes, and demographic surveys will be stored in a locked file cabinet until the study is completed. All participants will be provided with pseudonyms to protect their identity.

**Translation Plan:** The informed consents, child assents, brief demographic survey, recruitment materials (e.g. mail or emails from the healthcare provider, study brochure) and interview guides will be provided to participants in both English and Spanish, at the preference of the participant. The PI and I will translate all documents previously mentioned above and conduct English to Spanish translations or Spanish to English back-translations of the documents. After translation, both the PI and a bilingual PhD student will compare the original English version and the back-translated version to denote discrepancies and make revisions as necessary. The PI is of Cuban-American descent and is proficient in Spanish and conducted most of her research with primarily Spanish speaking participants. She has been translating documents for research purposes since 2001. The bilingual PhD student has achieved a level of proficiency in Spanish as indicated by advanced Spanish education (e.g., obtaining a minor or major in Spanish in college) and has experience conducting research with Spanish-speaking participants and assisting with back translation.

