## **SELECTION OF SUBJECTS**

Subjects will be identified in person at the Primary Care Pediatrics at Roxboro Road. I have gained permission from the selected clinic to conduct chart reviews and use the NCIR database to prescreen for eligible participants prior to their scheduled clinic visit. Eligibility will include: Adolescents ages 11 to 14 years who have received 1 dose of the HPV vaccine series between January 2017 and December 2017; parents as defined as the adolescent's biological mother or father, step-parents, or legal guardian; and, parents or legal guardians who self-identified as the primary caregiver of the adolescent child and most likely to make medical decisions for the adolescent. Only one parent or legal guardian and one adolescent per household will be included in the individual interviews. Exclusion criteria includes: Parents and adolescents with cognitive impairment, adolescents emancipated from their parents or legal guardian, and pregnant adolescent girls will be excluded from this study. Pregnant girls will be excluded from the study because the vaccine is not recommended for use in this population (CDC, 2016). Further, adolescents who did not receive any doses of the series are excluded since the focus of this study is to understanding barriers and facilitators to HPV vaccine completion.

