## **DATA ANALYSIS & STATISTICAL PLAN**

**Aim 1:** Descriptive statistics will be used to detail the characteristics and key measures for the eligible adolescents and their parents. Logistic regression will be used to determine the role that social determinants play in predicting HPV vaccine completion within 14 months. Individual-level determinants will be adolescent's age, sex, race/ethnicity, and insurance type; community-level determinants will be area deprivation index for residence and distance from clinic. Power calculations indicated a required sample size of 600 charts for adolescents who received the first dose of the HPV vaccine to achieve 80% power when conducting the primary analysis using multivariable logistic regression and supplemental regression analysis using Cox proportional regression models. This sample size estimate was based on the following assumptions: (a) up to 10 predictor terms in the final model; (b) medium effects, indicated by adjusted odds or hazards ratios; (c) two-tailed tests with significance set at 0.05 per test; and (d) an overall missing rate of less than 5% for terms in the model after imputation when needed. However, all charts that meet the eligibility criteria will be analyzed and it is estimated that the sample size will exceed the required sample size of 600 charts.

**Aim 2:** Directed qualitative content analysis will be conducted to examine parents and adolescents' experience with the HPV vaccine and barriers and facilitators to completing the vaccine series across level of determinant (e.g. individual, relationship, and community). For data integration, quantitative and qualitative data will be analyzed separately initially. Then, results from each separate analysis will be presented in data displays with an integrative summary for each level of determinant to assess patterns between quantitative and qualitative data and provide further description of the role that social determinants play on HPV vaccine completion.

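### The follow-up dates for Aim 1 describe a fixed calendar window, but the dose-interval rule counts from each adolescent's own first dose, and the plan does not reconcile the two

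*Combined protocol and SAP*

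**What the plan says.** All references are to the Combined protocol and SAP.

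- **DESIGN AND PROCEDURES, Procedures: Aim 1 (cohort and follow-up).** The cohort comes from the charts of "all adolescents ages 11 to 14 who received 1 dose of the HPV vaccine from January 2017 to December 2017". The next sentence dates the follow-up: "This cohort will be followed from January 2018 to February 2019 to assess vaccine completion within a 14-month period". No other text in the plan puts calendar dates on follow-up.
- **Same section, a few sentences later (derivation).** Here "the date of HPV vaccine administration will be used to determine the number of months between receipt of the first and second dose", again tied to 14 months. The worked example has the second "dose = 8 months from first dose". Dose dates are deleted once converted to months.
- **DESIGN AND PROCEDURES, Procedures: Aim 2.** The interview groups use the same limit, for example "16 parents and adolescents who did not complete the vaccine series (Non-completers) within 14 months will be recruited", without saying when the 14 months start.
- **Design paragraph; MEASURES; DATA ANALYSIS & STATISTICAL PLAN.** Each repeats the 14 months for the Aim 1 outcome with no time origin. The definition under MEASURES, Vaccine Completion, requires only that 2 doses were received, and adds that time to second dose will be collected. The analysis section plans logistic regression on completion and a supplemental Cox model, also without a stated origin.

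**The concern.** Completion within 14 months is the dependent variable of the primary logistic regression. Two people following different sentences of the same section could code it differently. A data manager working from the follow-up sentence would look for second doses between January 2018 and February 2019. An analyst working from the derivation sentence would take the interval between doses and compare it with 14 months.

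On the calendar coding, two adolescents with the same dose interval can receive different outcomes solely because they started in different months of 2017. If initiation month is related to any of the determinants studied, part of that coding difference would enter the odds ratios. The Completer and Non-completer interview groups in Aim 2 inherit the ambiguity, although less rests on it there because those samples are purposive.

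**Working it through.** **Inputs.** First doses: January to December 2017. Follow-up: January 2018 to February 2019. Limit: 14 months. All three are from Procedures: Aim 1. The 6 to 12-month schedule is from BACKGROUND & SIGNIFICANCE.

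**Step 1: reproduce the stated length.** Counting calendar months inclusively, 12 × (2019 − 2018) + (2 − 1) + 1 = 14. The figure of 14 therefore fits the calendar window itself.

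**Step 2: set the window against the personal clock.** Let a be the months from first dose to 1 January 2018. Read literally, the window runs from month a to about month a + 14 after the first dose. It covers 14 − a of the adolescent's own first 14 months, and a further a months beyond them.

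| First dose | a | Own first 14 months covered (14 − a) | Months beyond own month 14 (a) | Window closes at month (a + 14) |
|---|---|---|---|---|
| 1 January 2017 | 12 | 2 | 12 | 26 |
| 1 July 2017 | 6 | 8 | 6 | 20 |
| 31 December 2017 | 0 | 14 | 0 | 14 |

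By exact day count to 28 February 2019 (days ÷ 30.4375), the closing times are 788 ÷ 30.4375 = 25.9, 607 ÷ 30.4375 = 19.9 and 424 ÷ 30.4375 = 13.9 months. The rounded values hold.

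**Step 3: apply the plan's own example.** Take a second dose 8 months after the first. A first dose on 1 March 2017 puts it on 1 November 2017, before the window opens. A first dose on 1 September 2017 puts it on 1 May 2018, inside. Both are complete on the personal clock. The same mismatch affects any 8-month interval starting in January to April 2017.

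**Step 4: apply the stated schedule.** For a first dose on 1 January 2017, months 6 to 12 run from 1 July 2017 to 1 January 2018, so the whole scheduled interval precedes the window. From 1 July 2017 onward, none of it does.

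**Step 5: check the other direction.** A first dose in January 2017 and a second in January 2019 are 24 months apart, yet the second dose falls inside the window.

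**Step 6: check whether February 2019 is late enough for the personal clock.** A first dose on 1 January 2017 reaches 14 months on 1 March 2018, and one on 31 December 2017 does so on 28 February 2019. A day-by-day check of all 2017 dates found no personal period ending later. The end date works as a cut-off; the January 2018 start is what does not fit.

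**The case against.** The strongest defence is that the section, read as a whole, already favours the personal clock. The derivation sentence ties 14 months to the interval between doses. Deleting the dates leaves a dataset that could not support a calendar-window analysis unless a flag had been made beforehand, and none is planned. Time to second dose and a Cox model both sit naturally with the first dose as origin. February 2019 is 14 months after December 2017. All of this stands, and it makes the personal clock the better-supported reading. It does not explain the January 2018 start or say how late second doses count, and the derivation sentence describes an interval variable without expressly defining the binary outcome.

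A reader might go further in three ways that the documents do not support.

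- **That the plan excludes second doses given in 2017.** No sentence says so. The exclusion follows only if the follow-up sentence overrides the rest of its section, and it would sit badly with a completion definition that asks only for 2 doses.
- **That the cohort is restricted to adolescents with exactly one dose by the end of 2017, so that early completers are dropped.** The wording in the purpose statement ("among adolescents ages 11 to 14 who received one dose of the vaccine") and in SELECTION OF SUBJECTS ("Adolescents ages 11 to 14 years who have received 1 dose of the HPV vaccine series between January 2017 and December 2017") allows this in isolation. However, BACKGROUND & SIGNIFICANCE equates receipt of 1 dose with initiation, the selection criteria exclude those with no doses at all, and the analysis section refers to "charts for adolescents who received the first dose of the HPV vaccine".
- **That a misclassification percentage can be given.** That needs the distributions of first-dose dates and of dose intervals, and the plan supplies neither. The national initiation and completion rates in the background do not stand in for them: they mix 2- and 3-dose requirements and, as the plan says, do not describe this age group alone.

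**Conclusion.** The concern holds as an inconsistency in the outcome window. The follow-up sentence, as written, does not produce the outcome that the rest of the section appears to intend. Its literal application would observe between about 2 and 14 of an adolescent's own first 14 months, depending on the first-dose date, and would accept second doses up to about 26 months after the first. These figures are calendar arithmetic and assume nothing about dose intervals, but they apply only if the sentence is followed literally.

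The size and direction of any error in completion rates or odds ratios are unknown. Because the personal clock is the likelier intent and the planned data are sufficient for it, this should be fixed, but it is not a failure of the design.

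**What to change.** Reword the follow-up sentence in Procedures: Aim 1 to state that:

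- each adolescent's 14 months run from the date of their own first HPV dose in 2017;
- second doses given in 2017 count;
- second doses after the adolescent's own month 14 do not count as completion within 14 months;
- February 2019 is the data cut-off only.

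Carry the same definition into MEASURES, the Aim 2 grouping and the analysis section, and name the first dose as the time origin of the Cox model. Derive the completion flag from exact dates before they are deleted. The section's example labels the first dose as month 1, so whole-month coding could leave the 14-month boundary unclear.

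The cost is wording and one derivation step. Dose dates are already to be collected from the health record and the state immunization registry, and the planned cut-off covers every personal window, so no new data are needed provided the dates have not yet been deleted. The change concerns how the outcome is defined, not when doses should be given.
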